8. RESEARCH QUESTION AND OBJECTIVES

The aim of this study is to evaluate if individuals in the US with SCD treated with voxelotor receive fewer RBC transfusions compared to matched controls who are not treated with voxelotor. The research question for this study will be:

Among individuals with SCD and a history of RBC transfusions, do individuals
treated with voxelotor have a greater reduction in RBC transfusions per-patient-per
year (PPPY) between baseline and follow-up (up to one year after index date)
compared to matched SCD individuals not treated with voxelotor?

Objectives: Among individuals with SCD and a history of RBC transfusions, the following objectives will be compared between those treated with voxelotor and matched individuals with SCD who are not treated with voxelotor:

- Primary objective: Compare the change in RBC transfusions (PPPY from baseline [one year prior to index date] to follow-up [up to one year after index date]).
- Exploratory objective 1: 1.1 Compare the change in SCD-related complications including VOCs, ACS, and priapism (PPPY from baseline [one year prior to index date] to follow-up [up to one year after index date]); 1.2 compare the time-to-stroke during the follow-up period.
- Exploratory objective 2: Compare the number of RBC transfusions PPPY during the follow-up period (including those with 0 RBC transfusions). The percentage of patients with more than a 30% reduction in RBC transfusions from baseline will also be compared.
- Exploratory objective 3: Compare the time to RBC transfusion-associated complications (iron overload, iron chelation use, DHTRs, alloimmunization) during the follow-up period.

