Index Date1 Exposed: Prescription claim for voxelotor Inclusion Criteria (in prior 365 days): Control: Index date of voxelotor patient match ≥ 2 RBC transfusions Diagnosis of SCD **Exclusion Criteria:** Continuous Enrollment Stroke Pregnant at index Evidence of hemodialysis Continuous Voxelotor Evidence of hematopoietic stem cell transplantation or gene IO. 1801 therapy Inclusion Criteria Renal and/or liver transplant Inclusion/Exclusion Criteria 10.01 1-365, 01 Age ≥ 12 and ≤ 85 years Matching Criteria: Age **Patient Selection Matching Criteria** [0, 0] Covariate Assessment Period³ I-365, 01 **Outcome Assessment Period** [1. censor⁴] Start of study End of study period of interest November 2018 period of interest January 2024

Figure 1. Study Design Schematic

Abbreviations: RBC: Red blood cell; SCD: Sickle cell disease

 Index date for the exposed group will be the date of voxelotor prescription claim date and will be sequentially coarsened-exactmatched with up to 4 non-voxelotor patients based on age and calendar date.

Time

- Continuous voxelotor use defined using the voxelotor ship date and days supply with an allowable gap of at most 45 days (voxelotor arm only)
- 3. The full list of potential covariates including definitions can be found in Table 3.
- 4. Follow-up will end at the earliest of the following events: 365 days after index, death, disenrollment, the occurrence of any exclusion criteria events (e.g., pregnancy, stroke, hemodialysis, evidence of HSCT or gene therapy, renal transplant, or liver transplant), end of data, or discontinuation of voxelotor (voxelotor arm).

This study will use administrative closed claims data between November 2018 (one year prior to voxelotor FDA accelerated approval in the US) and the end of the study period (January 31, 2024; the matched controls will index on the same date of their matched

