9.7.3. Outcome Analysis

Operational definitions for each outcome are described below. Each outcome will be assessed using the primary assessment method for the follow-up period where follow-up will end on the earliest of the following occurrences:

- Disenrollment from health insurance (with a 45-day allowable gap)
- Death
- Discontinuation of voxelotor (with a 45-day allowable treatment gap, voxelotor arm only)
- End of follow-up: up to 1 year from index date (365 days)
- The occurrence of any exclusion criteria events (e.g., pregnancy, stroke, hemodialysis, evidence of HSCT or gene therapy, renal transplant, or liver transplant)

The primary analyses will employ an as-treated follow-up approach that ends follow-up upon treatment changes. Patients will be followed from the index date until treatment change (discontinuation of voxelotor for voxelotor group), or the end of follow-up, whichever is earlier. This as-treated method of analysis allows for an estimate of the effect while the patient is taking the drug of interest and addresses intercurrent events. However, it may introduce bias into the estimates. To adjust for differences in follow-up time between voxelotor patients and their matched controls, matched or pairwise censoring will be applied to censor unexposed on the date of voxelotor discontinuation for their matched pair as a sensitivity analysis.³⁸ A summary of sensitivity analyses is included in Table 7 to evaluate how the magnitude of this bias will be assessed.

Primary Objective - Change in Number of RBC Transfusions PPPY

For each patient, the difference in the number of RBC transfusions PPPY from baseline to follow-up period will be reported as the change and will be calculated as follows:

$$Change = \left(\frac{Number\ of\ RBC\ transfusions\ in\ follow-up}{Available\ days\ of\ follow-up} - \frac{Number\ of\ RBC\ transfusions\ in\ baseline}{365\ days\ *}\right)x\ 365$$

The change in the number of RBC transfusions PPPY will be analyzed using generalized linear model (GLM) with an identity link to estimate the difference in RBC transfusion change rates between the two groups. If any pre-index covariates that are found to be unbalanced after the PS method, it will be included in the regression as a covariate. The rate change and its 95% confidence intervals (CI) will be reported.

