$$Percent Change = \frac{(\frac{Number \ of \ RBC \ transfusions \ in \ follow - up}{Available \ days \ of \ follow - up} - \frac{Number \ of \ RBC \ transfusions \ in \ baseline}{365 \ days \ *} x \ 100}{\frac{Number \ of \ RBC \ transfusions \ in \ baseline}{365 \ days \ *}}$$

*All patients have 365 days of baseline data

The mean percentage change in the number of RBC transfusions PPPY within each group will be reported. The proportion of patients with a 30% reduction in RBC transfusions will also be reported for each group. A logistic regression model will be used to compare the difference of the proportion of patients with the reduction of more than 30% between the groups with an estimated odds ratio. The 95% CIs will also be reported.

Exploratory Objective 2 Endpoint 3 – Proportion of Patients with Zero RBC Transfusions PPPY in Follow-Up

This outcome will be defined as the proportion of patients with zero RBC transfusions PPPY during follow-up. A logistic regression model will be used to compare the percentage of patients without a transfusion in the follow-up time frame between the groups and an odds ratio will be estimated. The 95% CIs will also be reported.

Exploratory Objective 3 – Time to Transfusion-Associated Complications

Each RBC-associated complication (including the composite outcome) will be assessed as a time-to-event outcome. Cox PH models will be used to calculate the HR; 95% CIs will be calculated using a robust variance estimator. The Cox PH regression model may incorporate confounders that remain unbalanced after PS adjustment.

Sensitivity and Subgroup Analyses

Table 7 below includes a summary of the sensitivity analyses and the rationale for performing each analysis. The following sensitivity analyses will be performed for the primary endpoint unless otherwise specified:

Table 7. Planned Sensitivity and Subgroup Analyses

Analysis	Description	Rationale
Intention-to-Treat (ITT)	The follow-up period will be changed from astreated to follow an ITT approach with the exposed group requiring at least one voxelotor claim. All patients will be followed from the index date until disenrollment, death, or end of study period. Follow-up will not end on treatment discontinuation or switches.	To estimate the effect of the "assigned" treatment.

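### The ITT sensitivity analysis has no 365-day limit, so it changes the time horizon as well as treatment handling, and a difference from the primary result could not be attributed to as-treated censoring

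*Protocol*

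**What the plan says.** The research question in Section 8 compares the change in transfusions between baseline and "follow-up (up to one year after index date"), and the primary objective uses the same horizon. Section 9.7.3 applies one follow-up list to each outcome. Among its stopping rules are "End of follow-up: up to 1 year from index date (365 days") and "The occurrence of any exclusion criteria events", alongside disenrollment, death and, in the voxelotor arm, discontinuation. Footnote 4 of Figure 1 repeats the 365-day limit.

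The ITT row of Table 7 replaces that list: "All patients will be followed from the index date until disenrollment, death, or end of study period". It adds: "Follow-up will not end on treatment discontinuation or switches". It describes the cohort as "with the exposed group requiring at least one voxelotor claim", whereas Table 2 requires at least 180 days of continuous voxelotor use after index. The text below Figure 1 in Section 9.2 gives a calendar date for "the end of the study period (January 31, 2024").

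**The concern.** An ITT analysis beside an as-treated analysis is useful when the two differ mainly in how treatment after index is handled. The protocol relies on this comparison. Section 9.7.3 concedes that as-treated follow-up may bias the estimates and refers to Table 7 for the size of that bias. The treatment adherence row of Annex Table 3 names the as-treated and ITT analyses together as a check that results are consistent.

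As written, the ITT row also lengthens the horizon by an amount that depends on entry date, and it does not list censoring at exclusion events. If the two results differ, the reader cannot tell whether as-treated censoring, the later years or the exclusion events caused it. The outcome is a rate over each patient's available days, so later time off drug pulls an on-drug effect towards zero.

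**Working it through.** **Inputs.** Index period 25 November 2019 to 31 January 2023 (Section 9.2); end of study period 31 January 2024 (Section 9.2, below Figure 1); primary limit 365 days (Section 9.7.3).

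**The plan's own date.** 31 January 2023 + 365 days = 31 January 2024. The stated end date gives the last-indexed patient exactly one year, so a 365-day limit is feasible for every index date.

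**Maximum ITT follow-up as written.**

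- Index 31 January 2023: 365 days.
- Index 25 November 2019: 1,528 days; 1,528 / 365 = 4.19 years.
- If index dates were uniform (assumption), mean administrative follow-up would be (365 + 1,528) / 2 = 946.5, about 947 days. The share with more than two years available would be (1,528 − 730) / (1,528 − 365) = 69%. Both are before disenrollment or death.

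**Does the study end mean day 365?** Figure 1 footnote 4 lists 365 days after index as its own stopping rule, and the study end is given as a calendar date. On the text they are different things.

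**Effect of horizon alone.** The change is computed per patient as a follow-up rate minus a baseline rate; only the follow-up rate depends on the horizon. Suppose the effect is 1.0 transfusion per patient per year for the first t days on drug and zero afterwards, with follow-up of T days and no attrition. The annualised difference is then t / T. The protocol does not give t, so three cases are shown.

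| T (days) | t = 240 | t = 365 | On drug throughout, effect continues | Extra dilution against a 365-day cap (first two cases) |
|---|---|---|---|---|
| 365 | 0.66 | 1.00 | 1.00 | 365/365 = 1.0 |
| 700 | 0.34 | 0.52 | 1.00 | 700/365 = 1.9 |
| 947 | 0.25 | 0.39 | 1.00 | 947/365 = 2.6 |
| 1,528 | 0.16 | 0.24 | 1.00 | 1,528/365 = 4.2 |

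For any t up to 365 the extra dilution is T / 365 and does not depend on t. For patients who stay on drug with a continuing effect there is none. Because rates are formed per patient, the cohort figure is the average of 365 / T. With uniform index dates this is [365 / (1,528 − 365)] × ln(1,528 / 365) = 0.314 × 1.432 = 0.45. That is about 2.2-fold on average if everyone is off drug by one year, with no later effect and no attrition.

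**The case against.** The strongest reply is that a one-year reading is open. Table 7 analyses are for the primary endpoint, which is defined over one year. The ITT row presents itself as a change from as-treated follow-up, and the study end date is the last index date plus 365 days. Section 9.7.3 also sends details of potential sensitivity analyses to the SAP, which is not at hand. This leaves room for the cap to have been intended. It does not remove the conflict, because the row states its own end of follow-up, which the protocol elsewhere gives as a calendar date.

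Several stronger readings are tempting and not supported:

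- **That the ITT analysis cannot check the primary result at all.** The outcome is annualised, and under the dilution model above a longer horizon moves the estimate towards zero. An ITT effect in the same direction would still give some support.
- **That the missing limit unbalances the arms.** Under Section 9.2, controls index on the same calendar date as their voxelotor match, so the administrative maximum is the same within those matched sets.
- **That several-fold dilution is the expected size.** It needs everyone off drug by one year, no later effect and no attrition. The 1,528-day figure applies only to someone indexed on the approval date.
- **That the ITT analysis still runs on patients selected for 180 days of use.** The one-claim wording reads naturally as replacing that criterion and would otherwise be redundant. But the row describes only a change of follow-up period and does not say that the Table 2 criterion is lifted, so it merits a clarification.

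**Conclusion.** The point holds as an unreconciled follow-up rule in one sensitivity analysis. As written, ITT follow-up can last from 365 to 1,528 days by index date, against a one-year horizon in the primary objective and follow-up list, and exclusion-event censoring is not listed. The result is a changed estimand that depends on entry date. A difference from the primary result could not be assigned to as-treated censoring.

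Extra dilution relative to a 365-day cap ranges from none (index near January 2023, or patients still on drug with a continuing effect) to about four-fold (indexed at approval, off drug by one year, no later effect, no attrition). Time on drug, persistence of effect and the spread of index dates are assumptions; the date range itself rests only on the protocol. The primary analysis is not affected. The change should be made because the protocol relies on this comparison and the correction is small.

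**What to change.** In the ITT row of Table 7, end follow-up at the earliest of 365 days after index, disenrollment, death or end of data. Label any longer follow-up as a separate analysis. State in the row whether exclusion-criteria events end follow-up; if they do not, report that as a known difference from the primary analysis.

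In the same row, confirm that at least one voxelotor claim replaces the 180-day-use criterion of Table 2, and that age-and-date matching and the propensity score are re-run for that cohort. This matters because the reason given for the v2.2 change in Section 5 is that about 25-30% of voxelotor patients did not receive more than 30 days of treatment.

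Cost: the limit itself is one clause. Person-time after one year is not used in this analysis. The wider cohort needs one more matching run, with the propensity score diagnostics and study-team confirmation of Section 9.7.2 repeated.

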Required 1-year minimum follow-up	Two subgroup analyses have been proposed to evaluate bias introduced by differential follow-up. First, a subgroup analysis of patients with a minimum of 1-year of follow-up will be performed to evaluate the impact of informative censoring.	To address the impact of informative censoring and differential follow-up
Matched censoring	If meaningful differences in follow-up time are observed, matched censoring will be performed to assess the impact of differential follow-up between the exposed and referent group for the primary objective. Bias due to differential follow-up can arise when the reasons for participants dropping out or being lost to follow-up are related to both the treatment and the outcome. Matched censoring mitigates this bias by censoring all patients within a matched set (i.e., patients that have been matched by PS matching) at the earliest time in which a patient in the set was censored. In the context of 1:2 PS matching, where each exposed patient is matched to two referent patients, the matched set will consist of at most three individuals. Thus, matched censoring in this scenario involves censoring data for all three individuals in a matched set at the earliest observed censoring time among them.	To address the impact of informative censoring and differential follow-up
Stratification by number of RBC transfusions in baseline	The number of RBC transfusions PPPY in baseline will be categorized and the primary objective will be reported separately for those categories. This analysis will be performed for all objectives.	To understand the effect of the treatment on high-risk subgroups.
Subgroup analysis by Hb level	The primary analysis will also be performed on a subgroup of patients with Hb values at baseline. A separate PS model will be utilized for this subgroup.	To understand the effect of the treatment on high-risk subgroups and patients with available baseline data.
Subgroup analysis by prior medications	A subgroup analysis will be performed on patients who received hydroxyurea, crizanlizumab, L-glutamine, and/or ESA in baseline the exposed and referent groups.	To understand the effect of other SCD treatments.

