Because this study does not include an active comparator as a control group, CEM will be used to select the index date of matched controls on the initiation of voxelotor for exposed patients. All exposed patients will be selected prior to controls to preserve sample size. Sampling bias may be introduced by prioritizing exposures, but the impact is limited due to a larger pool of untreated control patients than potential exposures. There may be differences in patient characteristics dependent on when patients enter the study population (i.e., initiating voxelotor versus periods without treatment for matched controls). However, PS methods will be utilized to control for observed baseline confounding between the exposed and referent groups. Linked Ouest data will be used to evaluate Hb levels in baseline (an important diagnostic criterion for RBC transfusions). Feasibility analyses will be conducted prior to implementation to assess the number of patients in this study with available Hb data. Assuming a significant number of patients will not have Hb data in baseline, a sensitivity analysis has been proposed to assess the primary outcome among patients with this lab data. However, there may be differences in the frequency of Hb testing between the exposed and control group, relative to when patients enter the study cohort. For most subgroup analyses, the PS obtained from the overall study cohort PS model will be used for PS adjustment. However, for the subgroup of patients with non-missing Hb values in baseline, the PS model will be re-fit and will include an additional covariate (mean Hb value). Depending on the utilization of other SOC treatments in both the exposed and control groups, other subgroup analyses may be conducted. Additionally, the primary analysis will be as-treated, which includes discontinuation of voxelotor as a censoring criterion in the exposed group. This creates potential for confounding via differential censoring between the exposed and referent groups. However, to account for these potential differences in follow-up time, matched censoring will be used to censor matched controls on the date of their voxelotor match's discontinuation date as a sensitivity analysis.

A summary of the potential limitations of the RWD in this study and the mitigation strategies that will be applied is provided in Annex Table 3.

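### Table 7 credits matched censoring with mitigating outcome-related dropout, but the method corrects only for unequal follow-up windows

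*Protocol*

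**What the plan says.** The matched-censoring row of Table 7 (Section 9.7.3) describes bias that arises "when the reasons for participants dropping out or being lost to follow-up are related to both the treatment and the outcome". The next sentence begins "Matched censoring mitigates this bias by censoring all patients within a matched set", with the cut made "at the earliest time in which a patient in the set was censored". The rationale cell reads "To address the impact of informative censoring and differential follow-up". The 1-year minimum follow-up row carries the same rationale.

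The running text of Section 9.7.3 is narrower. It admits that the as-treated analysis may be biased and, to adjust for differences in follow-up time, plans to "censor unexposed on the date of voxelotor discontinuation for their matched pair as a sensitivity analysis". Section 9.9 says of voxelotor discontinuation as a censoring event: "This creates potential for confounding via differential censoring between the exposed and referent groups". It answers with matched censoring of controls, again described as accounting for follow-up time.

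Table 7 makes matched censoring conditional on meaningful differences in follow-up time. It also plans an ITT analysis in which discontinuation does not end follow-up.

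**The concern.** Discontinuation ends follow-up in the voxelotor arm only. If patients stop because of how their transfusions are going, the voxelotor rate is measured up to a point that depends on the outcome. Shortening the controls' follow-up neither recovers nor reweights the voxelotor time lost after such a stop.

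A close match between the as-treated and matched-censoring estimates could then be reported as showing that informative censoring is unimportant, because Table 7 says this is what the analysis addresses. The study reports are planned for FDA and EMA (Section 12), so the stated meaning of each sensitivity analysis matters.

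**Working it through.** **Inputs from the protocol.** Endpoint: per-patient events divided by available days, times 365, minus the baseline rate (Section 9.7.3). Discontinuation censors the voxelotor arm only (Section 9.7.3). At least 180 days of voxelotor use is required (Table 2) and follow-up is capped at 365 days, so discontinuation censoring acts between days 180 and 365. Sample size: 185 and 370 patients, SD 3.0, inflation factor 1.65, difference 1 (Section 9.5).

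**Inputs not in the protocol (assumed).** Follow-up transfusion rates, the share stopping after day 180, and why they stop.

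**Step 1: the plan's own figure.** The protocol states no figure for this bias, only the power. With two-sided alpha 0.05 (assumed):

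SE = 3.0 × √[1.65 × (1/185 + 1/370)] = 0.347

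Power = Φ(1/0.347 − 1.96) = Φ(0.92) = 82%, in line with the stated 80%. The SE of about 0.35 PPPY serves as a yardstick below.

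**Step 2: what matched censoring can change.** Under the controls-only rule, with the same sets and no covariate adjustment, the voxelotor mean is identical in both analyses. Hence:

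matched estimate − as-treated estimate = (control mean, full window) − (control mean, shortened window)

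A control is cut at a time T set by another person's stop. If the control's rate λ is constant, E[N(T)/T × 365] = λ for any such T, so the difference is zero in expectation. If λ varies over follow-up, the control mean becomes an average over a shorter window and the estimate moves. In neither case does the voxelotor term, where T depends on the patient's own course, change. The whole-set rule can only cut the voxelotor patient earlier still.

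**Step 3: Monte Carlo.** 40,000 voxelotor patients and 80,000 controls; control rate about 6/year; true difference about −1; gamma frailty; voxelotor stopping possible only after day 180. Bias is measured against the on-treatment difference over the full 365 days.

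| Setting | Stopped | As-treated bias | Matched-censoring bias |
|---|---|---|---|
| A. Stopping depends on a constant patient-level rate; flat rates | 34% | −0.01 | −0.01 |
| B. A transfusion triggers stopping; flat | 44% | +0.14 | +0.14 |
| C. Stopping as the patient's own rate worsens; flat on average | 30% | −0.26 | −0.27 |
| D. Stopping unrelated to outcome; rates decline in both arms | 53% | +0.31 | −0.06 |
| E. Decline plus transfusion-triggered stopping | 38% | +0.43 | +0.16 |
| F. Decline plus worsening-dependent stopping | 24% | +0.09 | −0.10 |

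Controls were not otherwise censored in A to F, so both rules give the same result. When random control censoring is added to B, the bias goes from +0.17 to +0.17 under the controls-only rule and to +0.13 under the whole-set rule.

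D shows the method doing its proper job. E shows the limit: the window part goes and +0.16 remains, close to the +0.14 in B.

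**Step 4: the neighbouring analyses.** A separate simulation with no drug effect, flat rates and outcome-related stopping gave, in two settings:
- as-treated: −0.06 and −0.09;
- matched censoring: −0.06 and −0.10;
- same patients followed to day 365 regardless of stopping: about 0;
- 1-year subgroup: −0.40 and −0.65.

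The subgroup does worst because it keeps only voxelotor patients who never stopped, so it selects on the stop itself.

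ITT does follow patients past discontinuation. As worded in Table 7, however, it also requires only one voxelotor claim instead of 180 days of use, and runs to the end of the study period instead of day 365. A gap from the primary estimate could come from any of the three changes.

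**The case against.** A reader might infer that matched censoring always returns the same biased estimate, and that the protocol therefore gives false reassurance about its primary result. The documents do not support that, for four reasons.

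- **The estimate does move when rates change over follow-up** (D, E and F). Such a trend is plausible, because patients are selected on at least two baseline transfusions, which invites regression to the mean. Near-identity holds only with flat average rates.
- **Sections 9.7.3 (running text) and 9.9 already describe the method as an adjustment for follow-up time.** The overclaim sits in Table 7.
- **Matched censoring is not the only safeguard.** ITT is planned, the protocol admits that the as-treated analysis may be biased, and further sensitivity analyses are left to the SAP, which is not shown. The absence of censoring weights is therefore no gap.
- **Neither size nor direction is established.** A harsher null model can be built: phases of 3 and 9 transfusions/year, with stopping 10 to 30 times likelier in the bad phase. It gives −0.46 to −0.78 as-treated and −0.46 to −0.81 across the two matched-censoring rules. But −0.33 to −0.55 of this remains when the same patients are followed to day 365. Only about −0.13 (−0.46 + 0.33) to −0.23 (−0.78 + 0.55) belongs to stopping after day 180. Setting B runs the other way, against voxelotor, and setting A gives about zero.

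All four stand, and they narrow the point. None of them supports Table 7's statement that matched censoring mitigates bias from outcome-related dropout, or the rationale it shares with the 1-year subgroup.

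**Conclusion.** The point holds in a limited form. Matched censoring addresses unequal follow-up windows and can remove most of that bias when rates change over time. It does not address voxelotor discontinuation related to the outcome, and nor does the 1-year subgroup. Table 7 says otherwise for both. Agreement between the as-treated and matched-censoring results should not be read as evidence against informative censoring. ITT is a partial check that cannot isolate the stopping rule.

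The part due to stopping after day 180 ranges in the illustrations from about −0.3 to +0.15 PPPY. At most that is roughly 0.8 of the design standard error (0.27/0.347) and about a quarter of the 1-transfusion difference the study is sized for. These sizes rest on assumed rates and stopping mechanisms. The structural result in Step 2 does not.

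**What to change.** 1. In Table 7, limit the matched-censoring description and rationale to differential follow-up length. Remove informative censoring from that row and from the 1-year minimum follow-up row.
2. Reconcile the controls-only rule (Section 9.7.3 text and Section 9.9) with the whole-set rule (Table 7). They give different results once controls are censored too.
3. Add one sensitivity run that keeps the primary matched sets and follows everyone to day 365 whether or not voxelotor is discontinued. Read it beside the as-treated and ITT results. It changes only the stopping rule.
4. Censoring weights with time-updated transfusions and acute-care claims are optional. In the two-phase simulation, weights built from recent claims recovered only a small part of the bias, so they should be supportive only.

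Cost: wording changes and one re-run on data already held. Downside: days after stopping dilute a true effect, so a gap from the as-treated estimate mixes loss of effect with informative stopping and must be reported as such.
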